8.1 Randomization

Patients that meet inclusion criteria will be randomized in a 1:1 ratio to either treatment or control group prior to beginning of the treatment cycle and stratified by age (lower or equal to 35 versus greater than 35). Allocation concealment will be ensured using a web-based random allocation sequence, which will require trial investigators to input patient information prior to receiving trial arm allocation.

8.2 Drug formulation, dosage, and reimbursement

The dosing and drug formulations are adherent to the care provided to our cancer patients seeking fertility preservation in our clinic.

Patients will undergo a random start of ovarian stimulation as per the standard of care in our clinic for all onco-fertility patients given that their treatment is time sensitive. Baseline estrogen, progesterone, LH, FSH, HCG levels are measured and a transvaginal ultrasound is performed and the stage of the cycle is determined. Ovarian stimulation will be performed according to results of the transvaginal ultrasound:

- Early follicular phase: FSH and rLH stimulation or FSH alone will be started as per randomization process. A GnRH antagonist will be given once the dominant follicle measures >1.4 cm.
- Mid to late follicular phase: patients who have a dominant follicle >1.5 cm with an E2 >300 and a progesterone <5 will be triggered with human chorionic gonadotropin (hCG, Ovidrel) 250 mcg subcutaneously. After three days, gonadotropin stimulation is started.
- Luteal phase starts: stimulation with FSH and Luveris or FSH alone, and once the dominant follicle measure >1.4 GnRH antagonist will be given.

Dosing:

- Recombinant luteinizing hormone (Luveris): daily dose of 75 IU subcutaneously.
- Follicular stimulating hormone (Gonal-F):
 - o If AFC < 15, FSH dose is 300 units
 - o If AFC > 15, FSH dose is 200 units
- GnRH antagonist dosing: either cetrorelix 250 mcg subcutaneous or ganirelix 250 mcg subcutaneously.
- Trigger of ovulation: Ovidrel 250 mcg or GnRH agonist (Suprefact 0.5 mg).

FSH dosing is based on a retrospective analysis of data from our centre. A multiple regression analysis found only AFC and AMH to be independently associated with higher number of mature oocytes. AMH is unavailable at the start of the treatment cycle as patients require to start chemotherapy immediately. Accordingly, FSH dosing will be based on AFC. Retrospective review of FSH dosing of our centre showed that when the AFC is less than 15, the majority of patients receive an FSH dose of 300 units to maximize the number of oocytes retrieved. When the AFC is equal to or more than 15, the majority of patients receive an FSH dose of 200 units to minimize the risk of ovarian hyperstimulation. FSH dosing in this trial will correspond to this dosing schedule.

Duration of treatment is guided by measuring serum biochemical markers including estrogen, progesterone, and LH levels. This in addition to monitoring follicular growth by transvaginal ultrasound to assess ovarian response to treatment. By participating in the study, patients will not be subjected to additional investigations or interventions that deviate from the standard of care provided to all our patients undergoing fertility preservation. Patients will not receive compensation for participation in the trial.

8.3 Study timeline

The duration of the trial, from the recruitment stage until completion, will vary depending on the amount of time needed to recruit patients for both arms of the study. Patients typically undergo a random start ovarian stimulation treatment, that ends with oocyte or embryo cryopreservation. Pregnancy rates are not part of the objectives of the study. Therefore, the timeline is expected to be between 2-3 months with each patient. The total duration of the study is expected to be 5 years (rounded up from 4 years 8 months) given 60% recruitment of 50 patients available at our site per year. Should fewer than expected number of patients be recruited at the 3-year mark, the study

period will be extended according to the observed annual recruitment calculated at 3 years for a maximum of 2 additional years.

8.4 Confidentiality

In order to protect the confidentiality of each participant, personal identifiers (such as date of birth and names) will be removed from the database and each participant will be assigned a random unique ID code to track their treatment outcomes. The aforementioned codes will only be accessible to the research coordinator of the study. This information will not be disclosed to any other individual or party without the written consent of the patient.

The information that is collected for the study will be kept in a locked and secure area by the study doctor for ¹⁵ years. Only the study team or the people or groups listed below will be allowed to look at your records. Your participation in this study also may be recorded in your medical record at this hospital.

The following people may come to the hospital to look at the study records and at your personal health information to check that the information collected for the study is correct and to make sure the study followed proper laws and guidelines:

- The study sponsor.
- Representatives of the Mount Sinai Hospital Research Ethics Board.

9. Safety

9.1 Discontinuation criteria and safety parameters

All patients undergoing a treatment of IVF at Mount Sinai Fertility are screened to ensure that they are in good health before starting a treatment cycle. All of our patients will be receiving a GnRH antagonist protocol which has lower rates of OHSS [27]. In addition, all patients in this study will have a freeze-all cycle, which will further minimize the risk of developing OHSS. There are preestablished protocols to monitor and minimize the risk of OHSS for any patient undergoing fertility treatment, including cycle cancellation prior to trigger, coasting, and/or administration of a dopamine agonist. All study participants will be extensively counselled about signs and symptoms of severe OHSS and advised to seek medical attention should they experience such signs or symptoms.

9.2 OHSS questionnaire

All study participants will be contacted by phone two weeks after completion of treatment using a standardized questionnaire to identify whether they experienced moderate-severe OHSS. The following script will be used:

I am going to ask you a few questions to determine whether you have experienced ovarian hyperstimulation syndrome, which is a medical condition caused by your body's excessive response to the hormones you received during your fertility treatment.

1. Have you experienced abdominal pain during your fertility treatment?

If yes, please describe the pain from a scale of 1 (no pain) to 10 (worst pain in your life):

- 2. Have you experienced abdominal distension during your fertility treatment?
- 3. Have you experienced abnormal nausea or vomiting?
- 4. Some patients may experience symptoms related to abnormal fluid collection in their abdomen. Did you have an ultrasound performed during your fertility treatment that revealed abnormal fluid collection in your abdomen?
- 5. Did you have an ultrasound performed during your fertility treatment that revealed abnormal fluid collection in your chest?
- 6. Did you experience any blood clots during your fertility treatment?

10. Adverse events

Patients will be counselled extensively about the potential symptoms of potential side effects of taking Luveris. The most common side effects experienced by around 2% of patients during clinical trials of the drug include but are not limited to the following: headache, pelvic and abdominal pain, nausea, breast pain, ovarian cysts, flatulence, injection site reactions, general pain, constipation, fatigue, painful menstruation, diarrhea and upper respiratory tract infections.

The most serious reported side effect is OHSS. Patients will be counselled extensively about the signs and symptoms associated with OHSS including but not limited to: nausea, vomiting, abdominal pain, abdominal discomfort, increased abdominal girth, bloating, decreased urine output, chest pain, shortness of breath, leg swelling, and/or pain. Subjects will be encouraged to contact the clinic if they have any concerns and seek immediate medical attention at the nearest hospital if they develop any of the aforementioned signs/symptoms.

Although extremely rare, potential serious adverse events related developing OHSS include:

- Development of ascites and/or pleural effusion
- Prerenal acute kidney injury
- A thromboembolic event such as a deep-vein thrombosis and/or pulmonary embolism
- Death

Any serious adverse event, directly attributed to the study medication, will be documented, managed and reported to the Mount Sinai Research Ethics Board immediately. In case of a rare event whereby a patient develops severe OHSS secondary to ovarian stimulation, further management may include:

- Hospitalization and/or extended hospital stay.
- Additional interventions such as a culdocentesis, paracentesis and, in rare circumstances, thoracentesis.
- Administration of the rapeutic or prophylactic doses of anti-coagulation medication.

11. Risk-benefit estimate

There is evidence supporting the benefits of adding rLH to FSH in patients with hypogonadotropic hypogonadism, and those who are poor responders and are of advanced maternal age. Several studies reported the concern about a possible lower ovarian reserve and lower ovarian response in a subgroup of cancer patients seeking IVF treatment. This may be partly explained by the theoretical concern that the hypothalamic-pituitary-gonadal axis is impacted by the underlying disease. Studies show conflicting outcomes in terms of ovarian stimulation outcomes in this study group. The potential benefit of rLH supplementation is that it will result in a relatively improved ovarian stimulation cycle, thus yielding more mature oocytes and embryos to be cryopreserved.

In our study, only patients with a diagnosis of a non-hormone sensitive cancer will be part of the study. Patients with a diagnosis of breast, uterine or ovarian cancer will be excluded from the study regardless of their receptor status.

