7.6 Outcome measures

The primary outcome measure will be the total number of mature (MII) oocytes adjusted by antral follicle count (AFC) available for cryopreservation.

Secondary outcome measures will include the following:

- Total number of oocytes retrieved per cycle
- Ratio of mature (MII) to immature oocytes
- Total number of mature oocytes (MII) retrieved per IVF/ICSI cycle
- Oocyte yield (defined as the number of metaphase II (MII) oocytes retrieved divided by the number of follicles ≥15 mm on ultrasound on the day of trigger)
- "Follicular Output Rate" (FORT) (defined as ratio of pre-ovulatory follicles (16-22mm) on day of trigger × 100/AFC (3-8mm) [22]
- Incidence of moderate to critical OHSS based on the classification criteria by Golan et al [26].
- If the embryos are frozen:
 - o Fertilization rate, which will include two outcomes each defined as follows:
 - Definition 1: number of 2PN zygotes divided by the number of mature oocyte(s) fertilized per IVF/ICSI cycle.
 - Definition 2: number of 2PN zygotes divided by the number of oocytes incubated with at least 10,000 sperm per IVF cycle.
 - Total number of good quality day 5 embryos available for cryopreservation determined by an embryologist using the classification system by Gardner and Schoolcraft, 1999 [25].
- Dose-adjusted evaluation of the safety and tolerability of follitropin alfa + lutropin alfa compared to follitropin alfa as measured by incidence of:
 - o Treatment-emergent adverse events (TEAEs)
 - Treatment-related adverse events (AEs)
 - o Incidence of thromboembolic events

8. Study methods

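### Adverse event incidence is a declared outcome, but the only scheduled safety contact is an OHSS call that leaves most listed Luveris side effects to spontaneous reports

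*Protocol*

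**What the plan says.** Section 7.6 of the protocol lists, among the secondary outcomes, the incidence of treatment-emergent adverse events (TEAEs), treatment-related adverse events and thromboembolic events. Section 5 names safety beside efficacy as a reason for the trial.

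The one scheduled contact for safety is in section 9.2: "All study participants will be contacted by phone two weeks after completion of treatment using a standardized questionnaire". Its stated aim is "to identify whether they experienced moderate-severe OHSS". The script has six questions: abdominal pain, abdominal distension, nausea or vomiting, fluid in the abdomen, fluid in the chest, and blood clots. None is a general adverse event question.

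Section 7.1 describes ultrasound and blood visits during stimulation. Their purpose is ovarian response, and no recording of adverse events is stated. Section 10 encourages patients to contact the clinic if concerned. It provides for documenting serious events that are directly put down to the study drug and is silent on other serious events.

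On cancer treatment, section 8.2 says: "AMH is unavailable at the start of the treatment cycle as patients require to start chemotherapy immediately". Neither the data list in section 7.5 nor the outcomes in section 7.6 include when cancer treatment began or what it was.

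**The concern.** An incidence can be compared between arms only if events are looked for in the same way in both. Here the plan declares the incidence of all treatment-emergent events as an outcome but actively asks only about OHSS. The remaining non-serious events enter only if a patient volunteers them, and patients know their arm. Two problems follow: events are missed, and they may be missed unequally.

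A second, smaller problem concerns nausea. By the time of the call some patients will probably have begun chemotherapy. The nausea question does not confine itself to the fertility treatment, and no recorded date would let anyone sort such reports afterwards.

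At stake is a declared safety outcome. The primary outcome, mature oocytes adjusted for antral follicle count, is not affected.

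**Working it through.** **1. Coverage of the script.** Section 10 lists 13 common Luveris side effects: headache, pelvic and abdominal pain, nausea, breast pain, ovarian cysts, flatulence, injection site reactions, general pain, constipation, fatigue, painful menstruation, diarrhea and upper respiratory tract infection. The script asks about abdominal pain and nausea. That is 2 of 13, so 13 − 2 = 11 are not asked about. A cyst might be seen on a monitoring scan, but nothing says it would be recorded as an adverse event.

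**2. Effect of spontaneous reporting.** Let the true rate of an unsolicited event be r in both arms, and let a share s1 (rLH arm) or s0 (FSH arm) of these events be reported. The observed rates are r·s1 and r·s0, and the observed difference is r(s1 − s0). Two consequences follow:
- If s1 = s0 < 1, both rates are too low.
- If s1 and s0 differ, a difference appears without any drug effect. Randomisation does not prevent this, because it arises after allocation. The protocol gives neither share.

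**3. Time limits in the script.** Five of the six questions are tied to the fertility treatment, for example "Have you experienced abdominal pain during your fertility treatment" and "Did you experience any blood clots during your fertility treatment". The third is not: "Have you experienced abnormal nausea or vomiting". Direct entry of chemotherapy symptoms is therefore mainly through that one question, plus recall error in the others.

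**4. What chemotherapy nausea does to the comparison.** Let the FSH arm have rate a, let rLH add d, and let chemotherapy independently cause the same symptom with probability q in both arms.
- FSH arm: 1 − (1 − a)(1 − q)
- rLH arm: 1 − (1 − a − d)(1 − q)
- Difference: d(1 − q)

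The documents give no a, d or q. As an assumption only, take a = 10%, d = 20 points, 63 per arm (section 12.1, before the allowance for loss) and a two-sided 5% test:

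| q | FSH | rLH | Difference | Power |
|---|---|---|---|---|
| 0% | 10% | 30% | 20 points | 81% |
| 20% | 28% | 44% | 16 points | 46% |
| 40% | 46% | 58% | 12 points | 27% |
| 60% | 64% | 72% | 8 points | 16% |

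With d = 0 the difference is 0 for every q. A simulation with 70 per arm and a = 10% gave a type I error of 4.9% to 5.2% over the same values of q. Equal chemotherapy exposure costs power and does not create a difference.

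**5. Scale of the expected events.** Section 10 speaks of around 2% of patients. If that applied to each symptom, 70 patients would give 70 × 0.02 = 1.4 events, and the chance of seeing at least one would be 1 − 0.98^70 = 76%. The rates in the table are far above this. They show the mechanism and are not a forecast.

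**The case against.** A reader might infer that effects of rLH cannot be told apart from those of chemotherapy. The documents do not support that. Patients are randomised 1:1 against a concurrent FSH arm (sections 7.1 and 8.1), so cancer treatment is balanced in expectation, and step 4 shows dilution without bias. Clots are no example of the problem either, because that question is tied to the fertility treatment. Even the nausea question follows an introduction about hormones received in fertility treatment, and some patients will read it in that light. What stands is dilution, and weaker attribution of single events.

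Section 8.3 says that "the timeline is expected to be between 2-3 months with each patient", and one might take this as an adverse event period reaching into chemotherapy. It describes how long a patient is in the study; no adverse event window is stated there.

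The absence of an adverse event item in section 7.5 proves little, since that list also omits oocyte counts and OHSS, which stand in section 7.6. The start of cancer treatment, however, is in neither place.

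Unequal reporting is a risk and not a demonstrated fact. Section 10 does not restrict its side effect counselling to one arm. But the counselling concerns a drug that only one arm injects, and patients know which arm they are in.

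That chemotherapy has begun by the call is an inference; section 8.2 gives no interval. Finally, the trial is exploratory, these outcomes are secondary, and events near 2% would be sparse in any case. TEAE definitions may properly sit in an analysis plan that is not at hand. Such a plan still cannot recover symptoms that were never asked about or dates that were never recorded.

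**Conclusion.** The point holds as a mismatch between the safety outcomes in section 7.6 and the collection described in sections 9.2 and 10. As written, 11 of 13 listed side effects are not solicited, and serious events not put down to the study drug have no stated route into the data. TEAE incidence will be under-ascertained and is open to differential reporting. The size of either effect cannot be derived from the protocol.

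The chemotherapy issue is narrower. It enters mainly through one question, shrinks a true difference by 1 − q, and hampers attribution of individual events in an open-label trial. It does not by itself produce a false difference between arms.

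The conclusion assumes that no separate adverse event form exists outside the protocol and that a material share of patients begin cancer treatment before the call. The second assumption matters only for the chemotherapy part. This should be corrected, but it does not threaten the primary analysis.

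**What to change.** - Ask the same short adverse event questions, including the section 10 symptoms, in both arms at oocyte retrieval and again at the existing call.
- Limit the nausea and vomiting question to the fertility treatment period, like the other five.
- Add start date and type of cancer treatment to section 7.5.
- Document all serious adverse events regardless of attribution, and record attribution as a separate item.
- Compare arms over a fixed window from first gonadotropin dose to the two-week call. Flag each event as before or after the start of cancer treatment, and add a sensitivity analysis restricted to events before it.

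The main window should not end at the start of cancer treatment. That start comes after randomisation, and a complication that delays cancer treatment would lengthen its own window. For the same reason the restricted analysis is supportive only.

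The cost is a few extra questions at two existing contacts and two data fields, plus entry of serious events that would otherwise not be recorded. No visit is added and clinical management does not change.

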A cohort study by Johnson et al. [16] examined the ovarian stimulation response in oncology fertility preservation patients under various IVF stimulation protocols which included the use of rLH in some patients. The study showed no overall difference in baseline measures of ovarian reserve, total dose of gonadotropin used, or mean number of oocytes retrieved in the group of 50 chemotherapy-naïve cancer patients compared to 50 matched healthy controls. Unfortunately, the number of patients receiving rLH and the total dose received by these patients was not specified. Other studies in the literature examining rLH included case reports and case series, with sample sizes insufficient to generate conclusions regarding rLH efficacy in cancer patients [17-19]. A systematic review concluded that research on ovarian stimulation protocols and outcomes in the onco-fertility literature was inconsistent and of low quality [20], calling for higher quality studies to provide clarity on this topic.

Therefore, we intend to conduct an exploratory randomized controlled trial (RCT) comparing FSH and LH versus FSH alone using a GnRH antagonist protocol in non-hormone sensitive cancer patients undergoing fertility preservation. These patients include those diagnosed with malignancy other than breast, uterine and ovarian cancer.

3. Study Question

In non-hormone sensitive cancer patients undergoing IVF fertility preservation, does the use of FSH and LH for ovarian stimulation lead to a greater proportion of mature oocytes available for cryopreservation relative to AFC compared to FSH alone?

We theorize that supplementation with FSH + rLH will increase the yield of mature MII oocytes among patients with non-hormone sensitive cancer undergoing fertility preservation compared to those with FSH alone. In addition, we anticipate the following trends among patients in the FSH + rLH group compared to those supplemented with FSH alone:

- Higher number of total oocytes retrieved per cycle
- Higher "Follicular Output Rate" (FORT), defined as ratio of pre-ovulatory follicles (16-22mm) on day of trigger divided by AFC [22]
- Higher number of cryopreserved embryos (if patient chooses to freeze embryos rather than oocytes)
- No significant difference in incidence of moderate-severe OHSS

5. Rationale

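### The phone script in section 9.2 cannot by itself grade the OHSS outcome of section 7.6, and the protocol links no other record to that grade

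*Protocol*

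**What the plan says.** Section 7.6 lists as a secondary outcome "Incidence of moderate to critical OHSS based on the classification criteria by" a cited published source. The expected trends set out after the Study Question (section 3) include "No significant difference in incidence of moderate-severe OHSS".

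Section 9.2 has every participant phoned two weeks after treatment ends, "using a standardized questionnaire to identify whether they experienced moderate-severe OHSS", and fixes the wording of six questions: abdominal pain (with a score), distension, nausea or vomiting, fluid in the abdomen, fluid in the chest, and blood clots. The two fluid items are "Did you have an ultrasound performed during your fertility treatment that revealed abnormal fluid collection in your abdomen" and "Did you have an ultrasound performed during your fertility treatment that revealed abnormal fluid collection in your chest".

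Section 10 calls OHSS the most serious reported side effect of the study drug. The signs it tells patients to watch for include "increased abdominal girth, bloating, decreased urine output, chest pain, shortness of breath, leg swelling, and/or pain". For severe OHSS it names hospital stay, anticoagulation and "Additional interventions such as a culdocentesis, paracentesis and, in rare circumstances, thoracentesis".

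**The concern.** The outcome is a graded diagnosis, and the only step the protocol describes for establishing it is a fixed script. If the script leaves out information needed to recognise a serious case, no later analysis document can recover it, because the question was never put. If a 'no' on fluid merges two different states, the incidence partly reflects who happened to be scanned.

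At stake is the comparison of the main safety risk of adding rLH. The protocol expects no significant difference in OHSS, and missed cases make that result easier to reach. The trial is open-label, so a decision to scan after retrieval could also be influenced by knowledge of the arm.

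**Working it through.** **Step 1. Section 10 against the script in section 9.2.**

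| Section 10 item | Asked in the call? |
|---|---|
| Abdominal pain; nausea or vomiting; girth or bloating | Yes (questions 1 to 3) |
| Decreased urine output, chest pain, shortness of breath, leg swelling | No |
| Ascites, pleural effusion (serious event) | Only if an ultrasound showed it (questions 4, 5) |
| Thromboembolic event (serious event) | Yes (question 6) |
| Prerenal acute kidney injury (serious event) | No |
| Hospital stay, drainage procedure, anticoagulation (management of severe OHSS) | No |

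The script covers some serious events and misses others. None of the three consequences that section 10 ties expressly to severe OHSS is asked.

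**Step 2. What a 'no' to questions 4 and 5 means.** Sections 7.1 and 8.2 provide transvaginal scans at baseline and during monitoring up to trigger, and retrieval is ultrasound-guided. No abdominal scan after retrieval and no chest scan at any time is scheduled. Section 8.2 says participation brings no investigations beyond standard care. Later imaging therefore depends on a clinical decision, and 'no' covers both a clear scan and no scan.

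**Step 3. Other records.** Section 7.5, the data-collection list, records cabergoline use to prevent OHSS but no OHSS event or grade. Section 7.6 makes treatment-emergent adverse events and thromboembolic events outcomes, without linking them to the OHSS grade. Section 10 commits to documenting and reporting serious events that are directly attributed to study medication. It also directs patients with symptoms to the nearest hospital, so an admission may lie outside the clinic's own file, and the call does not ask about it.

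**Step 4. Severity range.** Section 7.6 says moderate to critical; the expected trends and section 9.2 say moderate-severe.

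**Step 5. Direction of the effect, on assumed figures.** The protocol gives no OHSS rate and no power for this outcome, so there is no figure to reproduce. Section 12.1 supplies n = 70 enrolled and 63 evaluable per arm. Assume a true rate p and a share s of cases captured, equal in both arms.

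Expected recorded cases = n × p × s; chance of recording none in an arm = (1 − p × s)^n. With n = 70:

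| p | Cases, s = 1 | Cases, s = 0.5 | No case recorded, s = 1 | No case recorded, s = 0.5 |
|---|---|---|---|---|
| 1% | 0.7 | 0.35 | 50% | 70% |
| 3% | 2.1 | 1.05 | 12% | 35% |
| 5% | 3.5 | 1.75 | 3% | 17% |
| 10% | 7.0 | 3.5 | 0.1% | 3% |

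Power, by the normal approximation with n = 63 per arm, is Φ(z), where z = [|p2 − p1| − 1.96 × √(2p̄(1 − p̄)/n)] / √([p1(1 − p1) + p2(1 − p2)]/n) and p̄ is the mean of p1 and p2.

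- 5% against 15%, all captured: z = (0.10 − 1.96 × 0.0535)/0.0527 = −0.09, power 46%.
- Half captured (2.5% against 7.5%): z = (0.05 − 1.96 × 0.0388)/0.0386 = −0.68, power 25%.
- 5% against 10%: 18% with all captured, 11% with half captured.

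The approximation is rough with so few events. It shows the direction: equal under-capture moves the comparison towards no significant difference.

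**The case against.** The strongest defence is that the protocol never names the call as the sole source. The endpoint is defined by a classification, not by the questionnaire. A call meant to identify OHSS may be case-finding only. Adverse events are outcomes in their own right, section 9.1 refers to existing clinic protocols for monitoring OHSS, and patients are encouraged to contact the clinic. That is fair, and it rules out the claim that the endpoint cannot be obtained at all. What remains is that nothing connects those records to the grade.

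A reader might infer several stronger points that the document does not support:

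- *The script omits the markers of severe disease.* It omits several. Fluid and clots are asked, and a yes to questions 4 to 6 can flag a serious case. The omitted symptoms are listed as signs of OHSS in general, not of its severe form.
- *Some treated patients are never scanned.* The planned course scans them up to trigger and guides retrieval by ultrasound. The gap is later abdominal imaging and any chest imaging.
- *Unscanned patients will be recorded as free of fluid.* No coding of 'no' is stated. The fault is the ambiguity.
- *The pain score lacks a cut-off.* The script asks patients to "please describe the pain from a scale of 1 (no pain) to 10 (worst pain in your life" and links the score to no grade, but scoring rules may sit in an analysis plan that is not shown. This is not counted.
- *Ordinary discomfort will be counted as moderate OHSS.* The protocol states no such case definition, so no inflated incidence can be derived.
- *The script contradicts the cited classification.* Its criteria are not reproduced in the protocol, so this was not checked.

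**Conclusion.** The point holds in limited form. The section 9.2 script alone cannot grade the section 7.6 outcome. It leaves out signs and severe-disease consequences that section 10 itself names, its fluid items do not separate not scanned from scanned and clear, and no other record is tied to the grade. Cases can be missed, including those treated at another hospital.

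The size cannot be stated from the protocol. The figures above rest on assumed rates of 1% to 15% and an assumed half capture, and show direction only. Even with full capture, a trial of this size has limited power for OHSS. Scanning that differs by arm is possible in an open-label design, but nothing in the document gives its direction or extent. This is a low-cost improvement to one secondary safety outcome in an exploratory trial; the primary analysis is unaffected.

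**What to change.** 1. State in section 7.6 or 9.2 that OHSS is graded by the cited classification from existing clinic and hospital records and adverse event reports, and that the call serves as case-finding. Kidney injury and anticoagulation can be taken from the same records.
2. Add questions on shortness of breath, reduced urine output, an emergency visit or admission, and drainage of fluid. Chest pain can be a separate item at little further cost.
3. Split questions 4 and 5 into whether a scan was done and whether it showed fluid, and code no scan as not assessed.
4. Use one severity range in the expected trends, section 7.6 and section 9.2.

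The cost is a slightly longer call, some chart abstraction and a small amendment. The change concerns measurement only: it adds no scan or test and leaves clinical management untouched.

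### The OHSS call is made two weeks after treatment, but five of its six fixed questions, including all three on fluid and clots, ask only about the treatment period

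*Protocol*

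**What the plan says.** Section 9.2 sets the timing: "All study participants will be contacted by phone two weeks after completion of treatment using a standardized questionnaire". The stated aim is to find out whether participants had moderate-severe OHSS. The wording is fixed as well: "The following script will be used". The introduction tells the patient that the questions are meant "to determine whether you have experienced ovarian hyperstimulation syndrome", and gives no end date.

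Six questions follow. Those on pain, distension, abdominal fluid, chest fluid and clots each carry a treatment-period window, for example "Have you experienced abdominal distension during your fertility treatment", "Did you have an ultrasound performed during your fertility treatment that revealed abnormal fluid collection in your chest" and "Did you experience any blood clots during your fertility treatment". The question on nausea and vomiting carries none: "Have you experienced abnormal nausea or vomiting".

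Section 8.3 describes the course of treatment: "Patients typically undergo a random start ovarian stimulation treatment, that ends with oocyte or embryo cryopreservation". Section 7.6 lists moderate to critical OHSS and thromboembolic events among the secondary outcomes. Apart from this call, Sections 9.1 and 10 rely on counselling: patients are told which signs to look for, to contact the clinic with concerns, and to seek medical attention.

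**The concern.** A call made two weeks after treatment can pick up events from those two weeks. Five of the six questions do not clearly ask about them. A patient whose scan showed fluid, or who had a clot, ten days after her oocytes were frozen could truthfully answer no to questions 4, 5 and 6.

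This is the only scheduled contact after treatment that the protocol describes, and question 6 is the only scripted question on clots. What is at stake is the completeness of two named safety outcomes. The protocol anticipates no significant difference in moderate-severe OHSS. If events go unrecorded in both arms, a real difference becomes harder to see, so incomplete recording would tend to favour the anticipated result.

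**Working it through.** The protocol states no figure to reproduce here. The check is a count of the script's questions and a comparison of time points.

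**Step 1. Count the windows (Section 9.2).**

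| Question | Topic | Limited to the treatment period? |
|---|---|---|
| 1 | Abdominal pain | Yes |
| 2 | Abdominal distension | Yes |
| 3 | Nausea or vomiting | No window |
| 4 | Abdominal fluid on ultrasound | Yes |
| 5 | Chest fluid on ultrasound | Yes |
| 6 | Blood clots | Yes |

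- Limited: questions 1, 2, 4, 5 and 6, so 5 of 6.
- Fluid or clots (4, 5, 6): 3 of 3 limited.
- Symptoms (1, 2, 3): 2 of 3 limited.

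Question 3 cannot stand in for the others, because nausea shows neither fluid nor a clot.

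**Step 2. Place the end of treatment and the call on one time line.** Section 7.1 puts retrieval about 36 hours (1.5 days) after the trigger and has embryos cultured to day 5 or 6. I assume that oocytes are frozen on the day of retrieval and that treatment is complete at cryopreservation, as Section 8.3 suggests.

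- Oocyte freezing: treatment ends about 1.5 days after trigger; the call comes at about 1.5 + 14 = 15.5 days.
- Embryo freezing: treatment ends about 1.5 + 5 = 6.5 to 1.5 + 6 = 7.5 days after trigger; the call comes at about 20.5 to 21.5 days.

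On the literal reading, the five questions stop at about 1.5 days after trigger for one group and at about a week for the other. The following 14 days are not asked about in either. The period actually covered thus depends on what the patient chose to freeze.

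**Step 3. Compare with the other reading.** If the patient takes her fertility treatment to run up to the call, nothing is left out. The script does not say which reading applies. An introduction without an end date, one question without a window and five with one give her no consistent guide.

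**Step 4. Try to size the loss.** This would need the rate of moderate to critical OHSS and of clots, the share arising after cryopreservation, and the share of patients who read the phrase narrowly. The protocol gives none of these, so no number of missed events follows.

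**The case against.** The strongest reply is that the gap exists only on one reading. Section 8.3 is a sentence about the timeline, qualified as typical. It does not define the phrase used in the script, and patients will not see it. The same section expects 2-3 months with each patient. A patient who has just been told that the call is about OHSS may well mention fluid or a clot from the week before. This stands in part and is why the conclusion is that events may be missed, not that they will be. It does not remove the problem, because a standardized questionnaire should not depend on each respondent's interpretation. Section 9.2 itself treats treatment as completed two weeks before the call.

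Second, late events can surface in other ways. Patients are counselled on OHSS signs and encouraged to contact the clinic, and OHSS is graded by published criteria rather than by the script. This also stands in part. Those routes depend on the patient, and Section 10 sends patients with symptoms to the nearest hospital, so a later diagnosis may be made outside the clinic. That is the kind of event a scheduled call should bring to light.

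Third, Section 9.1 notes that the antagonist protocol and freeze-all cycles lower the risk of OHSS, and the trial calls itself exploratory. Both limit the likely impact.

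**Conclusion.** The point holds as a defect in a stated instrument: 5 of 6 questions, and 3 of 3 on fluid and clots, carry a window that on its literal reading closes two weeks before the call. Moderate to critical OHSS and thromboembolic events may be under-recorded. This rests on some patients reading the phrase narrowly and on some events arising after cryopreservation; the protocol quantifies neither. The primary outcome is not affected. The wording should be changed, mainly because the change is so cheap.

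A reader might infer three stronger things that the protocol does not support.

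- *That two full weeks of events are lost.* Fourteen uncovered days against none merely restates the two readings; it does not measure missed events.
- *That the arms are biased against each other.* The same script serves both arms. The trial is open-label, so differential reporting is conceivable, but nothing in the protocol shows it.
- *That Section 10 leaves events unrecorded unless they are attributed to the study medication, or shuts out control-arm events.* That sentence reads most naturally as a rule for immediate reporting to the ethics board and does not say that other events go unrecorded. Section 11.1, on funding, calls Luveris the intervention, but Section 7.1 lists Gonal-F in both arms and Section 7.6 names both drugs in the safety comparison. The term can readily cover both.

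**What to change.** In Section 9.2, give all six questions, including question 3, the same explicit window running up to the call, for example *since you started your fertility medications, up to today*. Define the start as the first medication of the study cycle, including any initial hCG trigger. That definition is needed because Sections 7.1 and 8.2 have some mid to late follicular starters receive hCG three days before gonadotropins, so a start tied loosely to the first injection would be ambiguous.

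The cost is a reworded script and slightly more event recording. No visit or call is added, and the sample size, primary outcome and clinical management do not change.
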